## **Objectives**

Effective control of chronic pain is a top priority in the United States, as approximately 10% of adults have severe chronic pain – most of which is chronic lower back pain (CLBP). However, despite the advances in neuroscience over the past 20 years, we still largely treat chronic pain with opiate narcotics, much as was done in the Civil War. In addition to their high abuse liability and dependence potential (1), only 30–40% of chronic pain patients declare they receive satisfactory (>50%) relief from their pain through pharmacological treatment (Attal et al., 2006). In these patients a common clinical practice is to escalate the dose of opiates as tolerance develops – which unfortunately has contributed to escalation in opiate overdose deaths (2), a resurgence of intravenous heroin use, and \$55 billion in societal costs (3). **Consequently there is a critical need for new, treatments that can treat pain and reduce reliance on opiates in individuals with chronic pain.**

**The goal of this R21 proposal is to evaluate 2 novel non-invasive brain stimulation strategies to mitigate pain and the brain's response to pain in CLBP patients that are currently taking chronic opiates, or that are seeking an alternative treatment for pain.** Transcranial Magnetic Stimulation (TMS), can induce long term potentiation (LTP-like) and long term depression (LTD-like) effects on brain activity in a frequency dependent manner. Our group has previously

demonstrated that LTP-like TMS to the dorsal prefrontal cortex (DPFC, a node in the Executive Control Network (ECN)) can decrease perceived pain and corresponding BOLD signal in the ‘Pain Network’ (7, 8, 10-12). The Pain Network is an expansion of the Salience Network (SN; insula, dorsal anterior cingulate) which includes the thalamus and somatomotor cortex(4-6). The analgesic effects of DPFC TMS can be blocked by naloxone – suggesting that the analgesic effects of LTP-like DPFC TMS are opiate mediated. Additionally, DPFC TMS delivered postoperatively leads to less patient administered morphine use (PCA-pump) in the hospital and less opiate use in the outpatient setting (9). **These data all suggest that LTP-like DPFC TMS is a promising candidate for treating pain (Strategy 1, Aim 1).**

The relative efficacy of these strategies will directly translate to development of a large clinical trial investigating rTMS as an innovative, new treatment option for pain in patients with CLBP.

## **Methods and Measures**

### **Design**

The proposed study will be the first to employ a randomized, double-blind, placebo-controlled design to parametrically evaluate the longitudinal effects of 16 days of rTMS to the DPFC (Aim 1) or the MC (Aim 2) on self-reported pain and the brain’s response to pain. This will be done in

a cohort of patients recruited from WFU clinics and the outer community with chronic lower back pain. Participants will be randomized to receive TMS to the DPFC, MC, or sham (50% at each site), using a Latin square randomization. Resting state connectivity will be collected at each MRI scanning session. Quantitative Pain Testing will be collected 11 times. MRI data will be collected 3 times: before the 1st visit of TMS, before the 12th visit of TMS, and before the 16th visit of TMS.

**Table 1. Study Design. Aim 1&2 will be conducted in parallel.**

^primary goal: evaluate 2 TMS strategies as tools to decrease acute pain and brain reactivity to pain.

^secondary goal: durability

Scr een ing	Group Assignment	Induction Phase				Maintenance Phase				Follow Up Phase						
		Week 1	2	3	4	5	6	7	8	9	10	11	12	13	14	15
	TMS Sessions	XXX	XXX	XXX	XXX	X	X	X	X							
	Clinical Assessments	XXX	XXX	XXX	XXX	X	X	X	X	X	X	X	X	X	X	X
	Quantitative Urinalysis	X	X	X	X	X	X	X	X	X	X	X	X	X	X	X
	Quantitative Pain Testing		X	X	X	X	X	X	X	X	X	X	X	X	X	X
	Neuroimaging			X					X							

### Setting

All study activities will take place at Wake Forest University of Health Sciences (WFUHS).

[name] primary office and research laboratory is located in the Clinical Neuromodulation Laboratory in the Department of Cancer Biology. [name] lab space will include a room dedicated for all research related activities including a space for screening participants and a space dedicated for TMS stimulation. It will contain a computer and desk for patient interviewing and a Magstim Bistim TMS system.

The MRI portion of the study will take place at the MRI center located on [name]. This will utilize the Siemens 3T scanner in the MRI center.

Finally, recruitment efforts will come from the local community using flyers as well as traditional and social media outlets (radio, television, Facebook, Craigslist, local newspapers). Collaborative efforts will be maximized in order to recruit subjects from associated WFU pain clinics and pain programs.

### Subjects selection criteria

**Participants.** We will enroll 48 men and women 18-75 years old with CLBP. These individuals may also have a history of current prescription opioid use (>3 months) for the treatment of pain. Participants will be recruited through WFU clinics as well as the outer community. Patients that have previously agreed to be contacted for research will be referred to the study or contacted via telephone. The risks of MRI and TMS to the unborn fetus are not well understood. Therefore, to be included, females must not be pregnant as determined by a urine pregnancy test and must be utilizing reliable birth control during the course of the study.

### Inclusion Criteria

1. Age 18-75 (to maximize participation)
2. Can currently be using prescription opiates
3. Has current chronic back pain (> 3 months)
4. Able to read and understand questionnaires and informed consent.

Protocol version: 3.0

Protocol date: 07/14/2020

5. Is not at elevated risk of seizure (i.e., does not have a history of seizures, is not currently prescribed medications known to lower seizure threshold)
6. Does not have metal objects in the head/neck.
7. Does not have a history of traumatic brain injury, including a head injury that resulted in hospitalization, loss of consciousness for more than 10 minutes, or having ever been informed that they have an epidural, subdural, or subarachnoid hemorrhage.
8. Does not have a history of claustrophobia leading to significant clinical anxiety symptoms.

### **Exclusion Criteria**

1. Any psychoactive illicit substance use (except marijuana and nicotine) within the last 30 days by self-report and urine drug screen.
2. Meets DSM-V criteria for current axis I disorders of obsessive-compulsive disorder, bipolar affective disorder, schizophrenia, dissociate disorders, eating disorders, and any other psychotic disorder or organic mental disorder.
3. Has current suicidal ideation or homicidal ideation.
4. Has the need for maintenance or acute treatment with any psychoactive medication including anti-seizure medications and medications for ADHD.
5. Females of childbearing potential who are pregnant (by urine HCG), nursing, or who are not using a reliable form of birth control.
6. Has current charges pending for a violent crime (not including DUI related offenses).
7. Does not have a stable living situation.
8. Suffers from chronic migraines.
9. Subject meets MRI and TMS exclusion criteria as measured by the MRI Safety Screen and TMS Adult Safety Screen, including (but not limited to) metal above the neck, history of traumatic brain injury, and history of seizures.
10. Participant does not have a stable phone number for contact through call and/or text.
11. Does not have a stable means of using WebEx (e.g. personal computer, Internet) for interaction with study personnel during COVID-19.

### **Sample Size**

A power estimate for Aim 1 and 2 was prepared using an original fMRI dataset previously collected in our laboratory (8). In this experiment, 18 healthy controls performed the same fMRI pain paradigm as the present study before and after a single session of 10 Hz rTMS. Mean parameter estimates for the “heat pain vs. rest” condition were extracted from several *a priori* regions of interest. These data yielded an effect size which ranged from 0.70 (thalamus) to 1.08 (insula) (n=15 yields 80% power using a two-sided p<0.05). Allowing for a 10% dropout rate after the screening visit, and up to a 20% dropout rate at the end of the Treatment phase (Week 4), as well as a 10% data loss rate for MRI (Aim 2) due to individuals with excessive head motion in the MRI scanner, screening 58 individuals should lead to complete data from 48 individuals (16 real DPFC, 16 real MC, 16 sham (50% at each site)). Randomization will be handled by a Latin Square design with replacement will be used to ensure even enrollment across groups with replacement. All individuals will be enrolled at WFUHS. Data analysis and quality assessment will be ongoing.

Due to several COVID related factors, including challenges with scheduling and hesitation that participants may have wearing a mask in the MRI scanner, some participants will not receive the MRI

portion of this experiment. This will not affect our total enrollment goals, nor compromise the scientific integrity of this study. Moreover, it will lower the risk associated with MRIs to these participants.

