**MRI scanning:** The MRI scanning session will last 30 minutes and will contain: 1) a high resolution anatomical image (T1-weighted MPAGE (TR 1.9 sec, TE 2.26 ms, 2x GRAPPA, 1 mm isotropic)), 2) resting state functional connectivity (TA 7 minutes, voxel size: 2.5 x 2.5 x 2.5, TR = 2.6 s, TE = 25 ms, flip angle = 60°, FOV = 224 mm x 224 mm, matrix size = 64 x 64), For each of the above strategies (Active rTMS or Active Sham) we will explore a series of SubAims designed to quantify the effects of rTMS on subjective pain, quantitative sensory testing, and brain reactivity to pain.

**SubAim 1- Evaluating Pain using Clinical Assessments and Quantitative Sensory Testing (QST):** Using the Medoc ATS pressure algometer (Medoc Ltd Advanced Medical Systems, Ramat Yishai, Israel), 3 primary outputs will be compiled for each individual via the method of limits (54): sensory threshold, pain threshold, tolerance threshold. The algometer has a rubber tip that will be pressed into the right forearm for the procedure. Participants will indicate when they first detect the pressure change (sensory threshold), when it becomes painful (pain threshold), and when they can no longer tolerate the stimuli (tolerance threshold). When participants indicate tolerance, the operator will release the algometer. QST will be performed at the following timepoints: for the first TMS visit, the QST will be administered prior to the first TMS session and immediately following the second TMS session; for the remainder of the TMS visits and follow-up visits, QST will be performed prior to the first TMS session at each visit. The acute changes for TMS visit 1 will give one measure for acute pain changes pre/post TMS. **Pain**

**Questionnaire.** In order to evaluate current levels of pain, we will ask participants to rate their current level of pain and discomfort (scale, 0 through 10), each time the participant comes in (Table 1). On days where the individual receives rTMS, they will fill out this assessment between each TMS session. **Pain and Craving Questionnaire:** In addition to the Pain Questionnaire above, participants will also rate their urge to use a pain reliever (Scale 0 – 10) and the amount they would be willing to pay for a pain reliever (in US Dollars). This questionnaire will be used at the same time during each intervention visit as the Pain Questionnaire (Table 2).

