**SubAim 2: Evaluating Pain using Neuroimaging Data** At baseline we expect that people with chronic pain will have elevated activations in the Pain Network. This will be analyzed through the resting state connectivity network. Following sham stimulation, we do not anticipate a significant reduction of this response. Based on prior studies by our group in non-opiate dependent individuals, following LTP-like stimulation of the DPFC, we expect a significant amplification of the DPFC (% BOLD signal change), and a reduction of the Pain Network (dACC, anterior insula) reflecting the increased influence of executive processes. MC TMS however will likely not have as large of an effect on ECN engagement during the instruction to Control the pain.

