- C. Neuroimaging Data (Aim 2):** Immediately following acquisition, functional structural data will be uploaded to a secure data server and converted to NIfTI format. All preprocessing and analyses will be performed using Statistical Parametric Mapping 12 (SPM12) in Matlab 2013 (Mathworks). Functional data will be corrected for magnetic field inhomogeneity and realigned (rigid-body, minimizing least squares differences) to the first image in the time series (Realign: Estimate and Unwarp). Non-linear deformations required for standard space normalization will be derived from each participant's anatomical image via a unified segmentation approach (Segment). After the mean realigned and unwarped functional image is coregistered to the skull stripped anatomical image (Coreg: Estimate) forward deformations (subject space to MNI standard space) will be applied (Normalise: Write). Finally, the data will be smoothed by an 8 mm full width half maximum Gaussian smoothing kernel (Smooth). Within-subject and between-group modeling. Data will be analyzed at the subject level using multivariate pattern analysis (Wager et al 2013 “An fMRI-Based Neurologic Signature of Physical Pain” new England Journal of Medicine). The six motion parameters (translations and rotations) will be included in the design matrices as covariates to account for non-task signal.

Resting State Connectivity will be measured to compare MRI scan 1 to scan 2 – immediately after the treatment. MRI scan 3 will also be compared to these scans to see if there is a sustainable reduction in pain activity between these networks. Additionally factor analysis will be used to investigate the durability of the effects of each strategy on functional connectivity in each of the 3 Core networks (SN, ECN, DMN) using factor analysis longitudinally. **Covariates:** As an exploratory analysis we will also quantify the impact of several covariates which have previously been documented to affect the brain response to pain and pain thresholds (sex, Becks Depression Inventory score, length of time using chronic opiates). Although all participants will have taken their daily dose of opiates, which has a stable pharmacokinetic profile, we will also consider time since last dose.

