**Exploratory Analysis:** We will evaluate if there are rate-dependent effects between baseline SN connectivity with the ECN and DMN and the efficacy of each TMS strategy on subjective pain. Data will be analyzed by using multivariate pattern analysis (MVPA) (2014). While the primary outcomes will be MRI V1 vs V2, we will also examine the relative ‘durability’ of the effects on pain by comparing the MRI data at the 1 month follow up between and within groups with factor analysis. **Integration of Brain based and Behavioral Based Outcomes with Gender and other Demographic Variables:** Finally, we will compare the relative efficacy of these two types of TMS using the behavioral and neuroimaging measures. Specifically, we will determine the effect sizes for DPFC and MC (relative to sham) stimulation on reducing the 1) the neural and 2) behavioral responses to pain, as well as 3) changes in clinical assessment metrics (see Approach). We will investigate the role of baseline cortical responsiveness on the pain response, as well as how changes in that evoked response are related to changes in both pain and craving measures. This will be specifically addressed as a factor of gender as

well, given that there are established differences in sensitivity to pain and prevalence of opiate dependence between men and women.

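### The single 80% power figure fits the largest quoted effect compared with sham but does not carry to 0.70, and its task-fMRI basis conflicts with the resting-state scan listed

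*Combined protocol and SAP*

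**What the plan says.** The Combined protocol and SAP has one power statement, in Sample Size: "These data yielded an effect size which ranged from 0.70 (thalamus) to 1.08 (insula) (n=15 yields 80% power using a two-sided p<0.05". Alpha and sidedness are given. The test, the SD that scales the effects, the effect to which the 80% belongs, and whether 15 means one arm are not. The section then aims for complete data in 48 people, 16 in each of the DPFC, MC and sham groups.

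The effects come from an earlier experiment in the same laboratory, in which "18 healthy controls performed the same fMRI pain paradigm as the present study before and after a single session of 10 Hz rTMS". The quantity extracted was a contrast of heat pain with rest.

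On this trial's own imaging:
- General Methods, MRI scanning, lists an anatomical T1 image and "resting state functional connectivity (TA 7 minutes".
- General Methods, SubAim 2, says of the Pain Network: "This will be analyzed through the resting state connectivity network".
- Outcome Measure(s), part C, says: "Resting State Connectivity will be measured to compare MRI scan 1 to scan 2".
- The Exploratory Analysis paragraph has "While the primary outcomes will be MRI V1 vs V2", and the text after it says "we will determine the effect sizes for DPFC and MC (relative to sham) stimulation on reducing the 1) the neural" response to pain.
- The COVID paragraph of Sample Size says that "some participants will not receive the MRI" component.

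**The concern.** When one power figure stands beside a range of effects, a reader can take it as the power for any region named in the sentence, including the thalamus at 0.70. Power changes a great deal between 0.70 and 1.08, and again between a before/after test and a comparison with sham. The plan mentions both kinds of comparison for imaging. A null thalamic result could then be read as a fair test at 80% power when the chance of detection was well below that. The pilot's results are meant to feed a subsequent R01, so the basis of the figure should be traceable.

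The second difficulty needs no power assumption. The effects were measured on a pain task that is called the paradigm of this study, but the scan list contains no such task.

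**Working it through.** **Inputs.** From Sample Size: two-sided alpha 0.05; d = 0.70 and 1.08; n = 15; planned 16 per arm. Not in the documents, so assumed: d is mean change divided by the SD of change (step 4 relaxes this). For the comparison with sham, sham shows no change and the SDs are equal.

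**Formulas** (noncentral t):
- Paired: df = n − 1, noncentrality = d√n.
- Two-sample, n per arm: df = 2n − 2, noncentrality = d√(n/2).
- Power is the probability that |T| exceeds the 97.5% point of the central t.

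**1. Reproduce the plan's figure.** Two-sample, d = 1.08, 15 per arm: noncentrality = 1.08 × √7.5 = 2.958, df = 28, critical value 2.048, power 81.5%. With 14 per arm it is 78.5%, so 15 is the smallest n per arm that reaches 80%. The figure reproduces at the top of the range. A paired test with n = 15 reaches 80% at d of about 0.78, which lies inside the range but is neither of the two quoted effects.

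**2. Carry it to 0.70.** For n = 15:
- Paired: 0.70 × √15 = 2.711, df = 14, critical value 2.145, power 71.3%.
- Two-sample: 0.70 × √7.5 = 1.917, df = 28, critical value 2.048, power 45.7%.

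**3. Both ends of the range.**

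| Comparison | 0.70 | 1.08 | 80% reached from |
|---|---|---|---|
| Paired, n = 15 | 71% | 97% | 0.78 |
| Paired, n = 16 | 74% | 98% | 0.75 |
| Change vs sham, 15 per arm | 46% | 81.5% | 1.06 |
| Change vs sham, 16 per arm | 48% | 84% | 1.03 |

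If the two real arms were pooled against sham (32 v 16), power would be 61% at 0.70 and 93% at 1.08. As a yardstick only, 80% at 0.70 takes 19 people for a paired test or 34 per arm compared with sham. If 14 per arm had usable MRI (an assumed number), power compared with sham would be 43% at 0.70 and 79% at 1.08.

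**4. If the source used the raw SD.** The effect on the change scale is d/√(2(1 − r)), where r is the pre/post correlation. The documents do not give r. For d = 0.70 and n = 15:

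| Assumed r | Effect on change scale | Paired | Compared with sham |
|---|---|---|---|
| 0 | 0.495 | 43% | 26% |
| 0.5 | 0.700 | 71% | 46% |
| 0.6 | 0.783 | 80% | 54% |
| 0.8 | 1.107 | 98% | 83% |

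At 0.70, 80% needs r of about 0.60 (paired) or 0.78 (compared with sham).

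**5. Source and trial side by side.**

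| | Source of the effects | This trial |
|---|---|---|
| Participants | Healthy controls | Chronic low back pain |
| Stimulation | One 10 Hz session | 16 days of theta burst |
| Imaging | Heat-pain task | T1 and resting state listed; Pain Network analysed by resting-state connectivity |

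Yet Sample Size calls the source task the paradigm of the present study. The Aim 1 and Aim 2 hypotheses (Objectives) and SubAim 2 also still refer to instructions to control the pain, and SubAim 2 to BOLD signal change.

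**The case against.** The strongest reply is that nothing is miscalculated. A quoted effect, an ordinary two-sample test and 15 per arm give 80%, and the text never claims 80% across the range. That stands. A reader might infer an arithmetic error, or a figure that cannot be reproduced; the documents support neither. Per arm is also the natural reading, because the section moves soon afterwards to 16 in each group.

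The 71% and 46% depend on a standardizer that the plan does not state. That also stands. With the raw SD and a high enough correlation, 0.70 would reach 80%. The shortfall is conditional, and the settling information lies in the laboratory's own dataset.

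A reader might take a within-arm paired test as the planned primary analysis. The documents do not say so. The references to visit 1 against visit 2 name time points, not a test. General Methods, Assessments, also takes the primary dependent measures from Quantitative Sensory Testing (QST), so the power figure does not describe everything the trial calls primary.

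The MRI list breaks off on a comma before unrelated text, so it may be incomplete. That is why the passages should be reconciled before anyone concludes that the task was dropped. Finally, Outcome Measure(s) says that the pilot exists to develop effect sizes. This lowers the consequence, but it does not supply the missing inputs.

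**Conclusion.** The point holds as a minor reporting fault. The 80% is correct for an effect of 1.08 compared with sham at 15 per arm, and the sentence does not confine it to that case. Under SD-of-change scaling, with no sham change and equal SDs, the planned 16 per arm falls about 32 points short of 80% at 0.70 for the comparison with sham, and about 6 points short for a within-arm test if one is planned. Under raw-SD scaling, power at 0.70 with n = 15 could lie anywhere from 43% to 98% (paired) or 26% to 83% (compared with sham) for r from 0 to 0.8.

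Separately, and without any such assumption, the effects describe a task outcome that the listed scan does not collect. For a resting-state outcome the power is at best indicative.

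A reader might conclude that the trial is underpowered and should be enlarged. The documents do not support that: the standardizer is unknown, the power figure concerns imaging only, and the stated purpose is to estimate effect sizes.

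**What to change.** First, check the laboratory's earlier dataset for the effect, test and standardizer behind the figure. Then replace the parenthesis in Sample Size. If the effects were scaled by the SD of change, wording such as this would serve:

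> With 16 analysable participants per arm and two-sided alpha 0.05, and assuming effects scaled by the SD of change, equal SDs and no change under sham, the comparison of change with sham has about 48% power at 0.70 and 84% at 1.08, reaching 80% from about 1.03. These figures concern the imaging outcome, not QST. They derive from heat-pain task fMRI in healthy controls and are indicative only if the imaging outcome is resting-state connectivity. Power falls if fewer than 16 per arm have usable MRI.

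If a within-arm visit 1 to visit 2 test is actually planned, name it and add about 74% at 0.70 and 98% at 1.08. If the raw SD was used, say so and recompute with the pre/post correlation in that dataset.

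Reconcile the claim in Sample Size that the paradigm is the same with the scan list and SubAim 2 in General Methods, and with the task-type hypotheses in Objectives and SubAim 2.

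The cost is wording plus one look at existing data. The downside is a less favourable stated power. No patients, visits or procedures are added.

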### **Interventions and Interactions**

**Participants.** We will enroll 48 men and women 18-75 years old with CLBP that may or may not have a history of current prescription opioid use (>3 months) for the treatment of pain. Participants will be recruited through the community along with WFU clinics. Patients that have previously agreed to be contacted for research and have current chronic pain will be referred to the study. Our prior history with targeted enrollment (See Significance) indicates this is feasible within 20 months, leading to full completion by 22 months. **Exclusion criteria:** Typical MRI and TMS exclusionary criteria, including metal above the neck or implanted in the body, use of prescription medications that lower seizure threshold, a history of seizures or traumatic brain injury, pregnancy or trying to become pregnant, current substance use or dependence (other than opioids and nicotine), history of seizure disorder, and claustrophobia. Participants will provide written informed consent following explanation of the study.

[figure not shown]

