**(b) Security of Participant Information**

For individuals that are enrolled in the study (invited for a screening visit) there will be two documents that contain their first and last names: the informed consent that includes the written

HIPAA authorization and a receipt for their compensation kept for tax purposes. Each of these documents will be kept in a separate 3-ring binder.

Each individual enrolled in the study will be assigned a unique patient ID number (starting sequentially from '100'). A folder will be created for each of these participants and labeled with their Patient ID number. The folder will contain the results of all of the testing for each individual. The patients will only be identified by number, not by name, on these documents. All information stored digitally for the enrolled participants will be labeled with the Patient ID number. As above all of the participant folders, along with the binders will be stored in a locked cabinet in [name] research laboratory.

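### Screening 58 does not yield 48 with complete data under the plan's own loss allowances: at the 20% ceiling about 38 or 42 have usable MRI

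*Combined protocol and SAP*

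**What the plan says.** The Sample Size section bases its power estimate on an earlier fMRI experiment in 18 healthy controls scanned before and after one rTMS session. It reports effect sizes from 0.70 (thalamus) to 1.08 (insula) for heat pain against rest, and states "n=15 yields 80% power using a two-sided p<0.05". It does not name a test or say whether 15 is per arm.

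It then lists the losses: "Allowing for a 10% dropout rate after the screening visit, and up to a 20% dropout rate at the end of the Treatment phase", a point it places at Week 4. A third loss, 10% of the MRI data, is labelled Aim 2 and attributed to head motion. Its conclusion is that "screening 58 individuals should lead to complete data from 48 individuals", split 16 real DPFC, 16 real MC and 16 sham. It does not show the arithmetic or say whether the 20% includes the 10%. It mentions replacement in connection with randomization but gives no further screening number.

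The next paragraph says that some participants will have no MRI for COVID-related reasons, gives no rate, and says that this will not affect enrollment goals "nor compromise the scientific integrity of this study".

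Elsewhere 48 has a different meaning. Subjects selection criteria says "We will enroll 48 men and women 18-75 years old with CLBP", and Interventions and Interactions repeats it. In those sections 48 is the number entering; in Sample Size it is the number finishing with complete data.

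**The concern.** A sentence that says it allows for certain losses should still hold when those losses occur. Here the last of the listed losses, the MRI loss, cannot be fitted into the step from 58 to 48 at all, and the Week 4 loss fits only if it is well below its ceiling.

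The consequence falls mainly on imaging. Imaging is the only outcome with a power statement, so it is where the planned number has to be right. The study is a pilot meant to supply effect sizes for a later grant (Outcome Measures). What is at stake is therefore an overstated imaging sample, not a failed confirmatory test.

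**Working it through.** **Inputs (Sample Size section).** Screened: 58. Target: 48 complete, 16 per arm. Loss after screening: 10%. Loss by Week 4: up to 20%. MRI loss: 10%. Equal allocation to three arms is assumed.

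**Trying to reproduce 48 from 58.** Two products come close, and each leaves out a listed loss:
- 58 × 0.8 = 46.4 omits the MRI loss.
- 58 × 0.9 × 0.9 = 47.0 omits any Week 4 dropout beyond the screening loss.

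Working backwards, 48 × 1.20 = 57.6, which rounds to 58. That may be how the figure arose, but the plan does not show it. Allowing for 20% loss requires dividing by the retained fraction, 48 / 0.8 = 60, and this still ignores the MRI loss.

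**All listed losses at the 20% ceiling.**

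| Reading of the 20% | At Week 4 | Usable MRI | Usable MRI per arm | Shortfall from 48 |
|---|---|---|---|---|
| On top of the 10% | 58 × 0.9 × 0.8 = 41.8 | 41.76 × 0.9 = 37.6 | 12.5 | 22% |
| Cumulative from screening | 58 × 0.8 = 46.4 | 46.4 × 0.9 = 41.8 | 13.9 | 13% |

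**Most favourable imaging case.** With no dropout beyond the 10% screening loss, usable MRI is 58 × 0.9 × 0.9 = 47.0 on either reading.

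**Non-imaging break-even.** After the screening loss, 58 × 0.9 = 52.2 remain. Reaching 48 at Week 4 requires further dropout of at most 1 − 48/52.2 = 8.0%. Counted from screening, the same limit is 1 − 48/58 = 17.2%.

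**Against n=15, read as per arm.** Fifteen per arm is 45 scans, which needs 45 / 0.9 = 50 participants at Week 4. The imaging set therefore falls below 15 per arm once more than 8 of the 58 are lost (13.8% in total, equivalently 1 − 50/52.2 = 4.2% after the screening loss). Both figures are inside the allowance. At the ceiling, 12.5 and 13.9 are both below 15.

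**Power, as illustration only.** Noncentral t, two-sided 0.05, with test and per-arm reading assumed:

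| n per arm | Two-sample, d=1.08 | Paired, d=1.08 | Two-sample, d=0.70 | Paired, d=0.70 |
|---|---|---|---|---|
| 16 | 84% | 98% | 48% | 75% |
| 13.9 | 78% | 96% | 43% | 67% |
| 12.5 | 73% | 94% | 39% | 62% |

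At n=15 and d=1.08 a two-sample test has 81.5% power, which is compatible with the plan's statement read per arm but does not prove that this was the calculation.

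**The case against.** **The 20% is a ceiling and the MRI loss is labelled Aim 2.** A reader might infer from the table that 58 cannot give 48 on any outcome. The documents do not support that. With further dropout of 8% or less, 48 non-imaging completers are reached, and on the cumulative reading the gap at the ceiling is only 1.6 people. This part of the objection stands and limits the point. It does not rescue 48 with complete imaging, which is missed even in the best case. The Aim 2 label does not help either, because the MRI loss is in the same list that leads to the 48.

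**Replacement.** If dropouts are replaced, 48 can be reached, but only by screening more than 58. The stated figure is still wrong.

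**Imaging as the primary outcome.** A reader might infer that the primary analysis is what suffers. The documents conflict. The exploratory paragraphs in Objectives and in the Exploratory Analysis call the comparison of MRI visits 1 and 2 primary, while the Assessments paragraph under General Methods takes the primary dependent measures from QST. The point does not depend on settling this.

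**Loss of power.** A reader might infer that imaging power drops to 73%. The documents do not support this as a statement about this trial. The effect sizes come from a heat-pain task, whereas the MRI scanning and SubAim 2 paragraphs describe an anatomical scan and resting-state connectivity. The source was a before-and-after experiment, so a paired test is at least as natural a reading, and at d=1.08 it stays at 94% or more. At d=0.70 power is below 80% even at 16 per arm, so attrition does not create that deficit.

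**Week 4.** TMS continues to Week 8, so one might add later losses. The plan gives no rate for them. The visit 1 to visit 2 comparison falls at about the twelfth session, the end of the induction phase in Table 1, so Week 4 is a reasonable point for that count.

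**Conclusion.** The figure of 48 with complete data from 58 screened is wrong under the losses the plan lists. At the ceiling the expected numbers are about 42 at Week 4 and 38 with usable MRI (sequential), or about 46 and 42 (cumulative). No reading gives 48 with complete imaging. The shortfall in usable MRI is 22% or 13%, before COVID-related omissions of unstated size, and the imaging set is below 15 per arm on both readings.

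The retention figures rest only on the plan's own rates and equal allocation. The comparison with 15 also rests on reading n=15 as per arm. For non-imaging outcomes the gap is conditional on dropout and may be small or absent. No loss of power for this trial's own scans has been shown. The statement that omitting MRI leaves scientific integrity intact has no support for the imaging comparison. This should be fixed, but it does not undermine a pilot whose purpose is to estimate effect sizes.

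**What to change.** - In Sample Size, say whether the 20% comes on top of the 10% or is cumulative from screening.
- Replace the step from 58 to 48 with the matching expected numbers at the ceiling: about 42 at Week 4 and 38 with usable MRI (12.5 per arm), or about 46 and 42 (13.9 per arm). State that these are before COVID-related MRI omissions.
- Make Sample Size, Subjects selection criteria, and Interventions and Interactions agree on whether 48 is the number enrolled or the number with complete data.
- Limit the scientific-integrity statement about omitted MRIs to the non-imaging outcomes.
- Do not carry the n=15 benchmark over to QST, which has no power calculation, and do not present the illustrative power values as applying to the resting-state scans.

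These are wording changes. The cost is that the stated numbers look less favourable and the team must commit to one reading of the 20%; recruitment does not change. Keeping 48 with usable MRI as a firm target would be a different choice: at the ceiling it means screening 48 / (0.9 × 0.8 × 0.9) = 74.1, so 75 (sequential), or 48 / (0.8 × 0.9) = 66.7, so 67 (cumulative), and that does add recruitment.
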